1.0 BACKGROUND AND RATIONALE

1.1 Study Synopsis

This is a non-randomized, prospective pilot study exploring the use of fluorothymidine (FLT)-PET-MRI in the evaluation of allogeneic bone marrow transplant patients to potentially predict engraftment success, malignancy relapse, and the development of graft versus host. A total of 12 patients who have undergone allogeneic bone marrow transplantation will undergo FLT-PET-MRI imaging on two separate occasions. The first scan will occur immediately after initial neutrophil count recovery on day +25. The second scan will occur on transplant day +60 by which time stable count recovery should have occurred. The findings on the first scan will be correlated with clinical outcomes and pathological results on transplant day +35, and the findings on the second scan will be correlated with clinical outcomes and pathological results on day +100. The day +35 and +100 time points were chosen because allogeneic transplant patients at our institution undergo a restaging bone marrow biopsy and aspirate with donor/recipient chimerism studies around these days as part of our usual standard of care. In addition to the 12 allogeneic transplant patients, 3 patients undergoing autologous stem cell transplant will also be imaged at the same two time points in order to determine how much of the FLT signal observed after allogeneic transplant is unique to that population and the result of allo-antigen driven T cell expansion.

1.1.1 Allogeneic HSCT and Graft-versus-Host Disease

Allogeneic HSCT is potentially curative for numerous high risk hematologic malignancies and offers several advantages over traditional chemotherapy. First, higher doses of cytotoxic chemotherapy and/or irradiation can be given since patients are subsequently rescued from the severe myelosuppression induced by the pre-transplant conditioning regimen by the infusion of healthy hematopoietic stem cells. Second and perhaps more importantly, mature T cells contained in the graft are able to mount immune responses against residual cancer cells surviving the conditioning regimen due to major and/or minor MHC disparities between the donor and recipient. Unfortunately, the allo-immune responses driving the GVL effect are typically not specific for malignant cells. As a consequence, donor immune cells attack normal host tissues resulting in a process known as acute graft-versus-host disease (GVHD). Acute GVHD is primarily T cell driven, usually occurs within the first few months after transplant, and results in skin rash, diarrhea, cholestatic liver damage, and, on occasion, acute lung injury.

The process by which donor T cells initiate the GVHD process has been extensively studied in animal models, and was reviewed previously.¹ In brief, naïve, “conventional” donor T cells (T_{cons}) traffic into recipient secondary lymphoid tissue

(spleen, lymph nodes, Peyer's patches) early after transplant, and undergo activation and expansion upon exposure to allo-antigens presented by *host* antigen presenting cells.² Donor T cells then migrate from host secondary lymphoid tissue (SLT) to peripheral GVHD "target organs", where they elicit tissue damage. The efficient homing of conventional donor T cells into recipient SLT appears to be *absolutely required* for GVHD pathogenesis in mice as recipient animals lacking all lymphoid tissue fail to develop GVHD following allogeneic transplantation.^{3,4} The relationship between donor immune cell expansion within host lymphoid sites and GVHD incidence in humans, however, has not been described.

Allogeneic HSCT patients are at risk for not only GVHD after transplant, but also poor stem cell engraftment and/or graft rejection which can ultimately lead to disease relapse. Currently there are no reliable methods for predicting in advance which allogeneic transplant patients are destined to develop graft failure/recurrent disease or GVHD. If, however, a radiographic approach could be developed to predict one or both of these outcomes, this would be extremely useful clinically. Both processes are modulated by immunosuppressive medications. Specifically, GVHD is prevented and treated with increased immunosuppression and graft failure is treated in the opposite manner. If an imaging modality could prospectively indicate the development of either of these processes during their earliest stages, this would allow the transplant physician to proactively tailor a patient's immunosuppression in order to hopefully improve transplant outcomes. Similarly, if an isolated site of disease relapse could be identified early, this could lead to directed tissue biopsy and the early initiation of pre-emptive chemotherapy and/or radiotherapy.

The current proposal explores the use of a novel imaging modality, FLT PET/MRI, to correlate allogeneic transplant outcomes with FLT and MRI findings during early stem cell engraftment and at a later time point following stable count recovery. Specifically, we will determine if the strength of the early FLT signal within the bone marrow correlates with engraftment success and if isolated areas of cellular proliferation within the marrow at a later time point might predict for leukemia relapse. In addition, based on the important role that host lymphoid tissues are known to play in GVHD pathogenesis in mice, we will determine if the FLT signal within host SLT after transplant can predict for the development of GVHD in human BMT patients. Because FLT imaging by itself cannot distinguish between bone marrow engraftment/proliferation and the allo-immune driven T cell expansion that ultimately results in GVHD, we will image autologous transplant patients as a comparator arm. Autologous HSCT like allogeneic transplantation involves the administration of very high doses of chemotherapy to high risk cancer patients in order to achieve better tumor kill. However, in this situation patients are administered their own cryopreserved stem cells to reconstitute the ablated hematopoietic system. Under those circumstances there is no allo-immune reactivity to drive T cell activation and expansion after transplant, and as a result there is no GVHD in the autologous transplant setting. Thus, these patients will help us to

elucidate how much of the FLT signal seen in the allogeneic setting is the result of allo-immune driven T cell expansion.

FLT-Imaging: Fluorodeoxyglucose (FDG)-PET detects the accumulation of FDG in glucose-avid tissue, and is a measure of overall metabolic activity. FDG is relatively simple to synthesize, has a long half-life (approximately 2 hours), and has a well-understood mechanism of uptake, making it the most commonly used radiotracer in oncology.^{5,6}

The diagnostic value of FDG-PET, however, is limited by its lack of specificity. There has been great interest in taking advantage of the various unique properties of tumor cells in PET imaging. Tumor and expanding inflammatory cells show increased DNA synthesis during cellular proliferation, making the DNA synthetic pathway an attractive target for their visualization.

FLT, an analogue of the pyrimidine thymidine, has recently become a PET imaging agent of interest due to its potential to image cellular proliferation. Briefly, FLT is taken up by specific nucleoside transporters on the cell membrane via facilitated diffusion, and subsequently phosphorylated by tyrosine kinase 1 (TK1). Once phosphorylated, FLT is metabolically trapped within the cell. Thus, ¹⁸F labeled FLT detection via PET provides a measure of TK1 activity, which is closely linked to the salvage pathway of DNA synthesis and cellular proliferation.⁷ ¹⁸F-FLT and ¹⁸F-FDG PET have the shared advantage of utilizing an ¹⁸F radiotracer with a 110 minute half-life, making ¹⁸F-FLT PET feasible in diagnostic PET sites without dedicated on-site cyclotrons. However, ¹⁸F-FLT PET addresses the limitations seen with ¹⁸F-FDG PET. Specifically, decreased background “noise” is seen with ¹⁸F-FLT PET, and confounding factors such as muscle uptake do not occur. The invention of PET/MR brings together the functional imaging capabilities of PET with the exquisite soft tissue discrimination of MR.

1.1.2 **FLT-Imaging in hematologic malignancies**

Previous studies have explored the use of FLT-PET imaging to evaluate bone marrow engraftment in both preclinical animal models and human autograft patients, and demonstrate the overall feasibility of the imaging approach in the HSCT setting. In work by Awasthi et al. a FLT signal was detectable in the bone marrow compartment of Wistar rats within 4 days of syngeneic HSCT, and was much more sensitive for early marrow engraftment than traditional FDG-PET imaging.⁸ In work by Woolthuis et al. the authors imaged 16 myeloma or lymphoma patients undergoing autologous HSCT transplant following high dose chemotherapy and compared them to non-transplanted controls.⁹ There, the investigators observed an enhanced FLT signal in the marrow compartment of transplant patients, with a relatively uniform distribution primarily seen in the spine and to a lesser extent the pelvis and proximal long bones. Conversely, in work by Agool et al. patients with various active hematologic malignancies underwent FLT-PET imaging prior to therapy.¹⁰ There, the FLT distribution

appeared to be more heterogeneous in appearance, with patchy areas of increased tracer uptake noted in patients with multiple myeloma, aplastic anemia, and myelodysplastic syndrome. Collectively, these data suggest that FLT-PET imaging is a sensitive tool for evaluating overall marrow recovery after HSCT, and that residual FLT activity as well as its overall distribution pattern after transplant could be a useful tool for monitoring for early disease relapse.

Importantly, however, none of these publications evaluated allogeneic transplant patients and none correlated FLT-PET imaging results with the subsequent development of GVHD, graft failure, or disease relapse. Furthermore, none have attempted to correlate FLT-PET results with simultaneous MRI findings which could also be used to predict engraftment success after transplant.

2.0 STUDY OBJECTIVES AND ENDPOINTS

Primary Objectives

- 2.1.1** To compare the overall FLT-PET bone marrow signal on transplant day +25 between allogeneic stem cell transplant recipients who do and do not go on to achieve complete donor bone marrow reconstitution by transplant day +35.
- 2.1.2** To compare the overall FLT-PET signal intensity within host secondary lymphoid sites on transplant day +60 between allogeneic stem cell transplant recipients who do and do not develop acute GVHD by transplant day +100.

2.2 Secondary Objectives

- 2.2.1** To compare the overall FLT-PET bone marrow signal on transplant day +60 between allogeneic stem cell transplant recipients who do and do not achieve complete donor bone marrow reconstitution by transplant day +100.
- 2.2.2** To compare the overall FLT-PET signal intensity within host secondary lymphoid sites on transplant day +25 between allogeneic stem cell transplant recipients who do and do not develop acute GVHD by transplant day +100
- 2.2.3** To evaluate differences in FLT uptake within the bone marrow and secondary lymphoid tissues in patients undergoing autologous HSCT versus allogeneic HSCT
- 2.2.4** To correlate the strength of the FLT-PET signal within the bone marrow on transplant day +25 with the rate of transfusion independence on transplant day +35 in allogeneic stem cell transplant recipients
- 2.2.5** To correlate the strength of the FLT-PET signal within the bone marrow on transplant day +25 with bone marrow cellularity on transplant day +35 in allogeneic stem cell transplant recipients.
- 2.2.6** To correlate the strength of the FLT-PET signal within the bone marrow on transplant day +60 with the rate of transfusion independence on transplant day +100 in allogeneic stem cell transplant recipients

- 2.2.7** To correlate the strength of the FLT-PET signal within the bone marrow on transplant day +60 with bone marrow cellularity on transplant day +100 in allogeneic stem cell transplant recipients
- 2.2.8** To evaluate if isolated or asymmetric foci of increased FLT within the bone marrow or lymph nodes on transplant day +60 are associated with the incidence of disease relapse by day +100 in allogeneic stem cell transplant recipients
- 2.2.9** To correlate the strength of the FLT-PET signal within the bone marrow on transplant day +25 and on day +60 with MRI findings suggestive of engraftment in allogeneic stem cell transplant recipients
- 2.2.10** To evaluate the association of the overall FLT-PET signal intensity within host secondary lymphoid sites on transplant day +60 with the overall incidence of acute graft versus host disease and malignancy relapse over the first transplant year

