2.3 Primary Endpoints

- 2.3.1** The overall FLT-PET bone marrow signal will be defined as the average maximum FLT SUV within the vertebrae, pelvis, and bilateral femurs measured at the time of early engraftment. This scan will be obtained on transplant day +25 +/- 5 days. Complete donor reconstitution will be defined as chimerisms $\geq 95\%$ within the CD3 and unfractionated compartments on bone marrow biopsy/aspirate obtained on transplant day +35
- 2.3.2** The overall FLT-PET signal within host secondary lymphoid tissue will be defined as the average maximum FLT SUV within the spleen, cervical lymph nodes, axillary lymph nodes, inguinal lymph nodes, and mesenteric lymph nodes. This scan will be obtained on transplant day +60 +/- 5 days. Acute GVHD will be diagnosed either clinically or preferably pathologically within any target organ by transplant day +100.

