2.4 Secondary Endpoints

- 2.4.1** The overall FLT-PET bone marrow signal will be defined as the average maximum FLT SUV within the vertebrae, pelvis, and bilateral femurs measured on transplant day +60. Complete donor reconstitution will be defined as chimerisms $\geq 95\%$ within the CD3 and unfractionated compartments on bone marrow biopsy/aspirate obtained on transplant day +100
- 2.4.2** The overall FLT-PET signal within host secondary lymphoid tissue will be defined as the average maximum FLT SUV within the spleen, cervical lymph nodes, axillary lymph nodes, inguinal lymph nodes, and mesenteric lymph nodes

on transplant day +25. Acute GVHD incidence will be diagnosed either clinically or preferably pathologically within any target organ by transplant day +100.

- 2.4.3** The overall FLT-PET signal within recipient secondary lymphoid tissue (average maximum FLT SUV within the spleen, cervical lymph nodes, axillary lymph nodes, inguinal lymph nodes, and mesenteric lymph nodes) and the bone marrow (average maximum FLT SUV within the vertebrae, pelvis, bilateral femurs) in autologous transplant recipients will be compared to the corresponding overall FLT-PET signals from allogeneic transplant recipients on transplant days +25 and +60.
- 2.4.4** Transfusion independence will be defined as not having received a packed red blood cell (PRBC) or platelet transfusion within the 7 days preceding the day +35 or the day +100 time point
- 2.4.5** Bone marrow cellularity will be defined in a dichotomous manner as either hypocellular or normocellular/hypercellular based on the bone marrow pathology report from the day +35 and day +100 bone marrow biopsies.
- 2.4.6** The average FLT SUV in the vertebral column will be compared to the quantitative T1 and Diffusion Weighted Imaging (DWI) signals in the vertebral column by MRI. The average FLT SUV in the pelvis will be compared to the quantitative T1 and Diffusion Weighted Imaging (DWI) signals in the pelvis by MRI. The average FLT SUV in the bilateral femurs will be compared to the quantitative T1 and Diffusion Weighted Imaging (DWI) signals in the bilateral femurs by MRI.

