8.2 Sample Size and Accrual

This is a pilot study to gather preliminary data, and the results from this study will be used to power a future larger R01. However, we will have power to detect large differences between groups as follows. For power calculation, the null hypothesis is that there will be no difference in the FLT bone marrow signal between those allograft patients demonstrating incomplete and complete donor reconstitution on their restaging marrow biopsies, and no difference in the FLT signal within secondary lymphoid tissues between patients with and without acute GVHD.

Complete Donor Reconstitution:

Considering only the 12 allogeneic patients, we will compare the mean FLT bone marrow signal between those with and without complete donor reconstitution. In general we would expect approximately 50-70% of our patients overall to achieve complete donor reconstitution in both the unfractionated and CD3 enriched compartments by transplant day +30.

Assuming equal number of patients with/without Complete Donor Reconstitution:

A sample size of 6 in each group will have 80% power to detect a probability of 0.854 that an observation in the Complete Donor Reconstitution group is less than an observation in the non-Complete Donor Reconstitution group using a Wilcoxon (Mann-Whitney) rank-sum test with a 0.100 one-sided significance level.

Assuming unequal number of patients with/without Complete Donor Reconstitution:

A total sample size of 12 will have 80% power to detect a probability of 0.87 that an observation in the Complete Donor Reconstitution group (n=7) is less than an observation in the non-Complete Donor Reconstitution group (n=5) using a Wilcoxon (Mann-Whitney) rank-sum test with a 0.100 one-sided significance level.

Graft Versus Host Disease:

Considering only the 12 allogeneic patients, we will compare the mean FLT signal within secondary lymphoid tissues in those patients who develop acute GVHD versus those who do not based on the criteria described previously. In general we would expect that approximately 30-40% of our patients will develop some degree of acute GVHD (any site and any clinical grade) by transplant day +100

A sample size of 6 in each group will have 80% power to detect a probability of 0.854 that an observation in the non-GVHD group is less than an observation in the GVHD group using a Wilcoxon (Mann-Whitney) rank-sum test with a 0.100 one-sided significance level.

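### The incomplete-reconstitution group in objective 2.2.1 can pool leukemia relapse with poor engraftment, and relapse may distort the marrow FLT comparison in either direction

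*Combined protocol and SAP*

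**What the plan says.** All references are to the combined protocol and SAP.

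- **Groups.** Objective 2.2.1 contrasts allogeneic recipients "who do and do not achieve complete donor bone marrow reconstitution by transplant day +100". Endpoint 2.4.1 requires chimerism of 95% or more in both the CD3 and unfractionated compartments of the day +100 marrow. Anyone below 95% in either compartment is incomplete, whatever the cause. Endpoint 2.3.1 uses the same rule at day +35 for primary objective 2.1.1.
- **Signal.** For 2.2.1 it is the "average maximum FLT SUV within the vertebrae, pelvis, and bilateral femurs measured on transplant day +60". The primary endpoint is built the same way: "The overall FLT-PET bone marrow signal will be defined as the average maximum FLT SUV".
- **Expected images.** Section 1.1.1 asks whether marrow signal strength goes with engraftment success, and also "if isolated areas of cellular proliferation within the marrow at a later time point might predict for leukemia relapse". Objective 2.2.8 tests isolated or asymmetric day +60 foci against relapse by day +100.
- **Analysis.** Section 8.3.1 plans rank-sum tests and ROC analyses, with no split, exclusion or sensitivity analysis for relapse.
- **Power.** Section 8.2 sets its one-sided alternative as the probability that an "observation in the Complete Donor Reconstitution group is less than an observation in the non-Complete Donor Reconstitution group". That puts the complete group lower.

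**The concern.** Chimerism shows whose cells are in the marrow, not why recipient cells remain. Recipient leukemia making up more than 5% of the unfractionated marrow would put a patient below 95%, alongside patients with poor or rejected grafts. On the background's reasoning, poor engraftment should give a weak marrow signal, while relapse may give hot foci. Because the signal averages regional maxima, a focus raises it.

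Section 8.2 expects 50-70% of patients to be complete, which leaves about 4 to 6 of 12 incomplete, so one patient carries real weight. A hot relapse could hide a true link between FLT and engraftment or, if the test is run as section 8.2 writes it, supply an apparent link that is really relapse. The same scan would count for 2.2.8 and be misread in 2.2.1. Section 8.2 says the results will be used to power a larger study, so a distorted effect size or ROC cutoff would carry forward.

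**Working it through.** **Inputs from section 8.2.** The test is specified "using a Wilcoxon (Mann-Whitney) rank-sum test with a 0.100 one-sided significance level". Two power statements are given: "A sample size of 6 in each group will have 80% power to detect a probability of 0.854", and for 7 complete versus 5 incomplete, "A total sample size of 12 will have 80% power to detect a probability of 0.87".

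**Step 1: reproduce the plan's power.** Noether's formula is N = (z_α + z_β)² / [12 c(1−c)(P−0.5)²], where c is the fraction in one group and (1.2816 + 0.8416)² = 4.508.

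- 6 versus 6, P = 0.854: N = 4.508 / (12 × 0.25 × 0.354²) = 11.99; power at N = 12 is 80.0%.
- 7 versus 5, P = 0.87: N = 4.508 / (12 × 0.2431 × 0.37²) = 11.29; power at N = 12 is 81.8%.

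The stated 80% reproduces. The exact test under a normal shift model gives 85% for both splits. For 7 versus 5 its attained level is 0.074.

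**Step 2: put one relapse among the 5 incomplete patients.** Assumptions:

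- Higher signal means better engraftment, as in section 1.1.1.
- Complete patients follow N(0,1) and poorly engrafted patients N(−d,1). Setting P = Φ(d/√2) = 0.87 gives d = 1.593.
- The 7 versus 5 split is borrowed from section 8.2, whose expectation concerns day +30. The plan states no day +100 split or power for 2.2.1.

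Let p_r be the chance that the relapsed patient's signal lies below a complete patient's. The pooled probability is (4 × 0.87 + p_r)/5. This is also the expected area under the ROC curve.

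| Assumed signal of the relapse | p_r | Pooled P | Exact power |
|---|---|---|---|
| No relapse | – | 0.870 | 85% |
| Recovers one third of the engraftment deficit | 0.774 | 0.851 | 80% |
| Recovers one half | 0.713 | 0.839 | 77% |
| Looks like an engrafted marrow | 0.500 | 0.796 | 66% |
| Raised as much as poor engraftment lowers it | 0.130 | 0.722 | 42% |
| Top rank of all 12 | 0 | 0.696 | 31% |
| Relapse left out (7 versus 4) | – | 0.870 | 82% |

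**Step 3: what full cancellation would need.** With equal and opposite shifts and k relapses among 6 (P = 0.854), the pooled P is [(6−k) × 0.854 + k × 0.146]/6, which is 0.736, 0.618 and 0.500 for k = 1, 2 and 3. The contrast vanishes only when half the incomplete group are relapses.

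**Step 4: the direction written in section 8.2.** If incomplete patients are truly higher with P = 0.87, one top-ranked relapse moves P to (4 × 0.87 + 1)/5 = 0.896 and power from 85% to 91%. Conversely, if the background is right and the test is run as section 8.2 writes it, power for the low-signal poor-engraftment pattern is about 0%.

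**Step 5: how likely is one relapse?** The documents give no rate. Assumed day +100 rates of 5%, 10% and 20% give 1 − (1 − q)^12 = 46%, 72% and 93% for at least one relapse among 12.

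**The case against.** The strongest counter-argument is that the plan does not consistently expect low signal in incomplete patients: section 8.2 writes the reverse, and there a hot relapse strengthens the contrast. This stands. It changes the direction of the distortion without removing it, and it shows that sections 1.1.1 and 8.2 disagree.

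Several other points stand in part:

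- The background and 2.2.8 tie relapse to a focal pattern, with hedging, and not to a high overall signal. One focus is diluted when regions are averaged, and the day +60 scan precedes the outcome by about 40 days. The milder rows of the table may therefore be nearer the truth than the 31%.
- The documents do not say that relapse takes chimerism below 95%. A small focal relapse might not, and would then not enter this group.
- Section 1.1.1 says poor engraftment or rejection can lead to relapse. Removing relapses conditions on a post-scan outcome and may remove the worst engraftment failures.
- Objectives 2.2.4 to 2.2.7 assess engraftment without chimerism, and 2.2.8 and 2.2.10 address relapse. None of these separates relapse within 2.2.1.

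A reader might infer that the opposite signals cancel and the comparison becomes null. Under equal and opposite shifts, that needs about half the incomplete group to be relapses, and the documents supply no rate that would make this expected.

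**Conclusion.** The point holds for 2.2.1 and its ROC analysis. The incomplete group is defined by chimerism alone, relapse is not separated, and the plan's own reasoning gives relapse a different image from poor engraftment. On the stated assumptions, one relapse among 5 incomplete patients takes exact power from 85% to somewhere between 31% and 80%, and the expected ROC area from 0.87 to between 0.70 and 0.85. In the section 8.2 direction, a top-ranked relapse raises power to 91%, and relapse could be read as a reconstitution signal. The range rests on an assumed number of relapses, an assumed signal for each, and the inference that relapse lowers chimerism below 95%.

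A reader might extend this to say that primary objective 2.1.1 is compromised, or that relapsed patients should be dropped from the main analysis. The documents support neither. Criterion 3.1.4 requires complete morphologic remission before transplant and the primary outcome is read at day +35, so the primary risk is smaller, though it cannot be quantified. Exclusion as the main analysis is a debatable trade, given the link that section 1.1.1 draws between poor engraftment and relapse.

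**What to change.** 1. In 2.3.1 and 2.4.1, use the restaging biopsy report to classify each allogeneic patient as complete, incomplete without relapse, or relapse. State which category applies if a relapsed patient's chimerism is still 95% or more.
2. Keep the all-patients comparison for 2.1.1.
3. For 2.2.1 and the reconstitution ROC, pre-specify complete versus incomplete-without-relapse and report it beside the all-patients result. Mark relapsed patients individually in the display and analyse them under 2.2.8.
4. Reconcile the one-sided alternative in section 8.2 with the rationale in section 1.1.1, and state the direction of the test before data are seen.

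The cost is endpoint wording and one category taken from biopsies already obtained as standard care; section 4.5 says relapse is collected routinely. The split comparison loses the few patients who relapse (85% to 82% power for one patient in the 7 versus 5 case) and conditions on a post-scan outcome, so both results should be shown.

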3.0 PATIENT ELIGIBILITY

3.1 Inclusion Criteria

- 3.1.1** Patients undergoing allogeneic bone marrow transplant for acute myeloid leukemia (AML), acute lymphoblastic leukemia (ALL), or myelodysplastic syndrome
- 3.1.2** Allogeneic transplant patients receiving either a fully myeloablative or reduced intensity chemotherapy +/- total body irradiation (TBI) conditioning regimen are eligible.
- 3.1.3** Allogeneic transplant patients receiving stem cells from a matched related, matched unrelated, mismatched unrelated, mismatched related (including haplotype matched) donors are eligible
- 3.1.4** Allogeneic transplant patients must be in a complete morphologic remission prior to transplant
- 3.1.5** Patients undergoing autologous bone marrow transplant for multiple myeloma
- 3.1.6** Myeloma patients must have achieved at least a very good partial remission prior to transplant and exhibit fewer than 10% plasma cells in their pre-transplant marrow biopsy
- 3.1.7** ≥ 18 years of age
- 3.1.8** Able to provide informed consent
- 3.1.9** Negative urine pregnancy test in women of child-bearing potential

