4.0 STUDY PLAN

4.1 Study Duration

It is anticipated that the total study duration encompassing recruitment, enrollment, and data analysis will take approximately 2 years. Active patient participation will last approximately 100 days. Patients will be followed for one year for the development of acute GVHD or graft failure.

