4.5 Medical Records Abstraction

Objectives of this study include identifying quantitative imaging markers that best predict engraftment quality and GVHD development in allogeneic HSCT patients. To achieve this aim, we will correlate the imaging data with the need for blood product transfusion support, biopsy based measures of bone marrow donor/recipient chimerism studies and overall bone marrow cellularity, and the clinical and/or histopathological documentation of graft versus host disease.

Patient pathology records will be obtained after the 100-day follow-up period has passed and again one year post-transplant or at the time of death if the patient expires prior to then

All patients receiving HSCT have outcomes data collected for quality and program performance assessments. This data is collected for every patient until either death or lost to follow-up. The data routinely collected includes demographic data, donor match information, and outcomes of engraftment, survival, disease relapse, and development of acute and chronic GVHD.

Image Analysis

Quantitative T1 and DWI ADC maps will be computed. Regions of interests (ROIs) will be drawn on the anatomic MR images (blinded to SUV values and clinical outcome), then transferred to FLT SUV maps. We will correlate the imaging data with the histopathological data to identify the quantitative markers that best predict engraftment quality.

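### Objective 2.2.8 sets the day +60 foci against relapse only to day +100; adding relapse through one year, which the trial already obtains, would give the analysis more events

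*Combined protocol and SAP*

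**What the plan says.** Section 2.2 holds two objectives on relapse.

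- **Objective 2.2.8** relates focal or asymmetric FLT uptake in marrow or nodes to relapse in the allogeneic recipients. The foci are those seen "on transplant day +60 are associated with the incidence of disease relapse by day +100".
- **Objective 2.2.10** relates the overall day +60 signal in secondary lymphoid sites to "acute graft versus host disease and malignancy relapse over the first transplant year". The foci do not appear in it.

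The reason for day +100 is in section 1.1: "The day +35 and +100 time points were chosen because allogeneic transplant patients at our institution undergo a restaging bone marrow biopsy".

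On follow-up and data sources:

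- Section 4.5: "Patient pathology records will be obtained after the 100-day follow-up period has passed and again one year post-transplant". The same section lists the outcomes routinely collected for every transplant patient until death or loss to follow-up: "outcomes of engraftment, survival, disease relapse, and development of acute and chronic GVHD".
- Section 4.1: "Patients will be followed for one year for the development of acute GVHD or graft failure". Relapse is not named there.

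On the population, section 3.1.4 states: "Allogeneic transplant patients must be in a complete morphologic remission prior to transplant". The allogeneic sample is 12 (section 1.1).

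No section gives a relapse rate, an expected number of relapses or a power figure for 2.2.8. Section 2.4 does not define relapse, and section 8.3 names no method specific to foci and relapse.

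**The concern.** Predicting relapse is one of the aims named in the synopsis (section 1.1). Section 1.1.1 proposes isolated marrow proliferation at the later scan as the sign that might do it. That sign is analysed once, and only over the roughly 40 days between the second scan and day +100. With 12 patients in remission before transplant, that window may well contain no relapse or just one, which leaves little or nothing to describe.

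The trial will also know about later relapses, because 2.2.10 needs them and section 4.5 obtains them. As written, no objective sets those later relapses against the foci. The pilot is meant to supply preliminary data for a larger study (section 8.2), and on this question it would supply less than its own data allow.

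**Working it through.** **Figures in the plan.** The only sample-size figures (section 8.2) concern the two primary comparisons. Noether's formula for the rank-sum test, N = (z_α + z_β)² / [12 c(1 − c)(P − 0.5)²], with one-sided α = 0.10, 80% power, c = 0.5 and P = 0.854, gives N = (1.282 + 0.842)² / (3 × 0.354²) = 11.99, matching 6 per group. For 7 versus 5 and P = 0.87 the formula gives 81.8% power, in line with the stated 80%. These figures are sound, but none of them covers 2.2.8.

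**Inputs for 2.2.8**

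- n = 12 (section 1.1), all assumed alive, relapse-free and under observation at the scan.
- Window to day +100: 100 − 60 = 40 days. With ±5 days on each time point (section 6.1) it is 30 to 50 days.
- Window to one year: 365 − 60 = 305 days.
- One-year relapse of 10%, 20%, 30% or 40%, with constant hazard. These are assumptions, since the documents give no rate.

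**Formulas.** Let S = 1 − one-year relapse rate. Expected relapses in t days = 12 × (1 − S^(t/365)). Chance of none = S^(12t/365).

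| Assumed one-year relapse | Expected, day +60 to +100 | Chance of none | Expected, day +60 to +365 | Chance of none |
|---|---|---|---|---|
| 10% | 0.14 | 87% | 1.0 | 35% |
| 20% | 0.29 | 75% | 2.0 | 11% |
| 30% | 0.46 | 63% | 3.1 | 3% |
| 40% | 0.65 | 51% | 4.2 | 0.6% |

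Worked case at 30%: 12 × (1 − 0.70^(40/365)) = 12 × 0.0383 = 0.46, and 12 × (1 − 0.70^(305/365)) = 12 × 0.2577 = 3.09. The chance of zero or one relapse by day +100 is about 99%, 97%, 93% and 86% across the four rows.

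**Sensitivity 1: late detection.** Scheduled marrows fall at days +35 and +100 only (section 6.1). A relapse arising between them but before the scan might first be found after it. Using 65 days (100 − 35) in place of 40, expected relapses become 0.22, 0.47, 0.74 and 1.04, and the chance of none 80%, 62%, 47% and 34%.

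**Sensitivity 2: no constant hazard.** Assume instead a cumulative relapse rate by day +100, which also counts relapses before the scan. At 5%, 10% and 15%, the expected number among 12 is 0.6, 1.2 and 1.8, and the chance of zero or one is 0.88, 0.66 and 0.44.

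**What so few events can show.** With no relapse, no association can be estimated. With one relapse among 12, and Fisher's exact test assumed because the plan names none, the best one-sided p is 1/12 = 0.083 if exactly one patient has foci, and at least 2/12 = 0.167 if two or more do.

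**The case against.** Day +100 is a reasoned choice. It is when every allogeneic patient has a restaging marrow, and section 6.1 schedules none later, so it is the last point at which marrow status is checked across the whole group. Sections 1.1.1 and 1.1.2 speak of finding relapse early, which suits a near-term window. This stands, and it is why day +100 should be kept. It does not explain why day +100 should be the only horizon.

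A reader might infer that the horizons have been swapped, with the relapse sign given the short window and the GVHD sign the long one. The documents do not support that. The lymphoid signal is also tied to day +100, in 2.1.2 and 2.2.2, and day +100 is the plan's common horizon for the second scan. Objective 2.2.10 adds a one-year look, and the foci simply lack the same addition.

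A reader might also infer that a null result would reflect only the short window. It would reflect the small sample too, and about 1 to 4 events at one year would still support description only. Nor does the plan bar an unplanned one-year look at the foci.

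The event counts are assumption-driven. Deaths or relapses before day +60, and later deaths without relapse, would lower them. An early-concentrated hazard would narrow the contrast between the windows.

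Finally, a time-to-relapse analysis would need a method that section 8.3 lacks, as well as a rule for death without relapse. A simple one-year incidence needs much less.

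**Conclusion.** The gap holds as a matter of text: 2.2.8 is the only objective that uses the foci, it stops at day +100, and one-year relapse is already obtained for 2.2.10 and under section 4.5. Under a constant hazard with all 12 patients at risk and one-year relapse of 10% to 40%, the expected number of relapses after the scan rises from about 0.1–0.7 to about 1–4. The direction is secure, because a longer window cannot contain fewer relapses. The size of the gain depends on rates the documents do not give, and the two sensitivity checks show that it could be smaller.

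The omission of relapse from section 4.1 is a separate inconsistency with 2.2.10 and 4.5. It should not be read to mean that one-year relapse data would be lost, since those two places already provide for them.

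This is a cheap improvement to one secondary objective of a pilot. The primary analyses are not affected.

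**What to change.** 1. **Objective 2.2.8.** Keep the day +100 analysis. Add the incidence of relapse after the day +60 scan through one year post-transplant, among patients relapse-free at the scan, by presence or absence of foci. Starting the count at the scan also settles whether relapses before it are included.
2. **Section 8.3.** State that the one-year result is descriptive, with deaths without relapse shown separately. If time to relapse is summarised, treat such deaths as a competing event.
3. **Section 4.1.** Add relapse to the one-year follow-up sentence so that it agrees with 2.2.10 and 4.5.

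The cost is an amendment to the wording, a little more analysis, and a wait for the one-year data that 2.2.10 already requires. No visit, scan, biopsy or data source is added. Because no marrow is scheduled after day +100, later relapses will come from the pathology and routine outcome records, and the report should say so.
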